3.6.3 Screening and Risk Assessment by CLL-TIM

The investigator assumes the responsibility of obtaining written informed consent for each patient for the screening part before any study-specific procedures are performed. Assessment of variables for the risk profile including the baseline characteristics, pathology results, prior medical history and medical history including infectious events along with laboratory results will be performed based on the web-based CLL-TIM algorithm accessed at cll-tim.org. Patients will be assigned a unique screening ID, and the entered data along with the web-based CLL-TIM risk assessment will be part of the eCRF system. To allow for central review of CLL-TIM profile and baseline CLL characteristics, up to 4 weeks of response time is allowed and a screening period up to 6 weeks (42 days) before randomization is allowed. Approval of enrollment by the study office is mandatory before randomization and initiation of study treatment. Additionally, the study office will notify the sites if a patient is potentially at increased risk for development of TLS based on the baseline assessments. Patients not assessed as high risk by CLL-TIM, either assessed as low risk or as low confidence for prediction, will be followed by local medical record reviews and/or registries for 6-monthly assessment of infectious events, treatment initiation and overall survival.

3.6.4 Enrollment and Randomization Procedures

The investigator assumes the responsibility of obtaining written informed consent for each patient for the treatment before any study-specific procedures and randomization is performed. A central medical review of the screening CRF pages and the results of the baseline results in the central laboratories will be performed by study physicians for verification of the eligibility of the patient, especially for confirmation of the CLL diagnosis.

Randomization has to occur within 42 days of the tests for screening, however results included for the CLL-TIM assessment, which were obtained as part of routine care for the patients may be included even prior to randomization. FISH analysis for cytogenetic aberrations and TP53 mutational assessment should be within 6 months of randomization. Patients will be randomly assigned to treatment vs observation through 1:1 randomization process with stratification

according to country, TP53 aberration status and IGHV mutational status. Treatment or observation period has to be initiated within 14 days of randomization.

3.7 STUDY DRUG

3.7.1 Premedications for Patients Randomized for Treatment

Due to risk of tumor lysis, all patients have to initiate allopurinol 300 mg once daily from one day prior to start on treatment until at least start of cycle 3; whether continuing allopurinol until end of cycle 3 is on the discretion of the treating physician. In the case of allergy to allopurinol, probenecid or rasburicase may be used as alternatives on the discretion of the treating physician. Sufficient oral hydration, at least 2 L per day, is required during venetoclax ramp up.

3.7.2 Formulation, Packaging, and Storage, Acalabrutinib

The investigational product, acalabrutinib capsules for oral administration, is supplied as yellow and blue, opaque hard gelatin capsules, with 100 mg of acalabrutinib as the active ingredient. Each capsule also contains compendial inactive ingredients: silicified microcrystalline cellulose, which is composed of microcrystalline cellulose and colloidal silicon dioxide, partially pregelatinized starch, sodium starch glycolate, and magnesium stearate. The capsule shell contains gelatin, titanium dioxide, yellow iron oxide and indigotine (FD&C Blue 2).

Acalabrutinib will be provided in white, high-density polyethylene bottles.

Acalabrutinib will be shipped to trial sites labeled as an Investigational Medicinal Product.

Acalabrutinib will be prepared and labeled in compliance with GMP and other applicable regulatory

requirements.

Acalabrutinib should be stored and handled in accordance with the instructions in the Investigator's Brochure. The investigational medicinal product should be stored in such a manner that accidental loss or destruction or access by an unauthorized person is prevented.

The sponsor will arrange delivery of Acalabrutinib to trial sites. No investigational medicinal product will be shipped until the sponsor has verified that all regulatory required documents and approvals for the site are available. Acalabrutinib will be dispensed to subjects in bottles at each visit.

Refer to the acalabrutinib Investigator Brochure for additional information regarding the drug product to be used in this trial.

3.7.3 Administration of Study Drug, Acalabrutinib

Acalabrutinib capsule is administered 100 mg BID and taken orally approximately every 12 hours.

The capsules should be swallowed intact with water. Subjects should not attempt to open capsules or dissolve them in water. Acalabrutinib can be taken with or without food.

If a dose is missed, it can be taken up to 3 hours after the scheduled time with a return to the normal schedule with the next dose. If it has been > 3 hours, the dose should not be taken, and the subject should take the next dose at the scheduled time.

Guidance on co-administration of acalabrutinib with agents that affect gastric pH is provided in Section 3.12.2.

3.7.4 Formulation, Packa ging, and Storage, Venetoclax

Venetoclax is available in tablets of 10, 50 or 100 mg.

Venetoclax will be shipped to trial sites labeled as an Investigational Medicinal Product. Venetoclax will be prepared and labeled in compliance with GMP and other applicable regulatory requirements.

Venetoclax should be stored and handled in accordance with the instructions in the Summary of Product Characterization. The investigational medicinal product should be stored in such a manner that accidental loss or destruction or access by an unauthorized person is prevented.

The sponsor will arrange delivery of venetoclax to trial sites. No investigational medicinal product will be shipped until the sponsor has verified that all regulatory required documents and approvals for the site are available. Venetoclax will be dispensed to subjects in blister packs through the dose ramp up period, and in bottles at each subsequent visit.

3.7.5 Administration of Study Drug, Venetoclax

Patients should take venetoclax tablets orally once daily (in the morning) according to the schedule below, please see section 3.9 for management of modifications and tumor lysis risk:

Agent	Dose/day	Route of administration	Cycle	Days
Venetoclax	20 mg	Orally	1	1-7
Venetoclax	50 mg	Orally	1	8-14
Venetoclax	100 mg	Orally	1	15-21
Venetoclax	200 mg	Orally	1	22-28
Venetoclax	400 mg	Orally	2-3	1-28

Patients should be instructed to drink plenty of water daily starting 2 days before and throughout the dose-titration phase. Patients should be particularly instructed to drink 1.5 to 2.0 L of water daily, 2 days prior to and the days of dosing at initiation and each subsequent dose increase. Patients should avoid consumption of foods or beverages containing grapefruit or Seville oranges or starfruit, as these contain certain ingredients that inhibit CYP3A activity.

If the patient misses a dose of venetoclax within 8 hours of the time it is usually taken, the patient should take the missed dose as soon as possible on the same day and resume the normal daily

dosing schedule. If a patient misses a dose by more than 8 hours, the patient should not take the missed dose and should resume the usual dosing schedule the following day.

If vomiting occurs even with all expelled tablets still intact, no replacement dose is to be taken that day. The next dose should be taken at the usual time the following day.

3.7.6 Assuring Subject Compliance

The investigator, or a pharmacist or other appropriate individual who is designated by the investigator, should maintain records of the product's delivery to the trial site, the inventory at the site, the use by each patient, and the return to the sponsor or alternative disposition of unused product(s). These records should include dates, quantities, batch/serial numbers, expiration dates (if applicable), and the unique code numbers assigned to the investigational product(s) and trial patients (if applicable). Investigators should maintain records that document adequately that the patients were provided the doses specified by the protocol and reconcile all investigational product(s) received from the sponsor. The investigator should also collect and count remaining medication, empty boxes and blisters of medication to check that the patient has taken the assigned dose.

3.8 STUDY TREATMENT SCHEDULE

Acalabrutinib will be administered orally 100 mg twice daily, every day from cycle 1 day 1 for 3 cycles of 28 days each.

Venetoclax, ramp up during the first five weeks starting cycle 1 day 1, 7 days treatment on each dose level (20-50-100-200-400 mg), thereafter 400 mg once daily for a total of 3 cycles of 28 days counted from cycle 1 day 1.

Please see section 3.9 for management of dosing delays and modifications.

3.9 DURATION OF THERAPY

Duration of treatment with acalabrutinib and venetoclax is for 3 cycles of 28 days; the end of trial is defined as seven years after start of treatment or observation with close follow up for the first two years, while follow up for AESI's, CLL treatment and survival continues until end of trial. The primary endpoint for the phase 2 part is 6 months after start of treatment or observation.

3.10 DOSING DELAYS AND MODIFICATIONSIn the case of AEs attributed to both acalabrutinib and venetoclax, the local investigator should decide whether dose

modifications apply to one or both drugs in collaboration with the sponsor, as no data on pharmacokinetic interaction between acalabrutinib and venetoclax are currently available.

3.10.1 Dosing Delays and Modification for Acalabrutinib

Subjects should be followed closely for AEs or laboratory abnormalities that might indicate acalabrutinib-related toxicity. If a subject experience a treatment-related toxicity or other intolerable AE during the course of therapy, then acalabrutinib should be withheld, as necessary, until the AE resolves or stabilizes to baseline or at least grade 1 toxicity.

Acalabrutinib may further increase the risk of hemorrhage in patients receiving antiplatelet or anticoagulant therapies and patients should be monitored for signs of bleeding. Acalabrutinib should be withheld for 3-7 days pre- and post-surgery depending on the type of surgery and the risk of bleeding.

Dose modifications for the following treatment-emergent toxicities are provided in Table 3-X:

- Grade 4 neutropenia (< 500/μL) for > 7 days (neutrophil growth factors are permitted per American Society of Clinical Oncology (ASCO) guidelines and use must be recorded on the case report form [CRF]).
- Grade 3 thrombocytopenia in presence of significant bleeding.
- Grade 4 thrombocytopenia.
- Grade 3 or 4 nausea, vomiting, or diarrhea, if persistent despite optimal antiemetic and/or anti-diarrheal therapy.
- Any other Grade 4 toxicity or unmanageable Grade 3 toxicity.

Example Table 3-X: Drug Modification Actions for Acalabrutinib

Occurrence	Action
1 st – 2 nd	Hold acalabrutinib until recovery to Grade ≤ 1 or baseline; may restart at original dose level
3 rd	Hold acalabrutinib until recovery to Grade ≤ 1 or baseline; restart at one dose level lower (100 mg QD), may re-escalate to full dose on the discretion of the treating physician as detailed below
4 th	Discontinue acalabrutinib if not fully re-escalated 4 th occurrence, otherwise as for 3 rd occurrence

As appropriate, certain laboratory abnormalities may warrant more frequent monitoring (eg, once per week) until abnormalities have recovered to Grade ≤ 1 . If acalabrutinib is reduced for apparent treatment-related toxicity, the dose need not be re-escalated, even if there is minimal or no toxicity with the reduced dose. However, if the subject tolerates a reduced dose of acalabrutinib for ≥ 4 weeks then the dose may be increased to the next higher dose level, at the discretion of the

investigator. Such re-escalation may be particularly warranted if further evaluation reveals that the AE that led to the dose reduction was not treatment-related. The maximum dose of acalabrutinib is 100 mg BID.

Treatment with acalabrutinib should be withheld for any unmanageable, potentially study drugrelated toxicity that is Grade ≥ 3 in severity. Any other clinically important events where dose delays may be considered appropriate must be discussed with the Principal Investigator.

3.10.2 Dosing Delays and Modification for Venetoclax

Dose modification for TLS and other toxicities.

Dose at interruption (mg)	Restart dose (mg ^a)
400	300
300	200
200	100
100	50
50	20
20	10
aThe modified dose should	

before increasing the dose.

For patients who have had a dosing interruption lasting more than 1 week during the first 5 weeks of dose titration or more than 2 weeks after completing the dose-titration phase, TLS risk should be reassessed to determine if restarting at a reduced dose is necessary (e.g., all or some levels of the dose titration).

Venetoclax Recommended Dose Modifications for Toxicities

Event	Occurrence	Action				
Tumor Lysis Syndrome						
Blood chemistry changes or symptoms suggestive of TLS (Cairo-Bishop grading in Appendix 6)	Any	Withhold the next day's dose. If resolved within 24-48 hours of last dose, resume at the same dose.				
		For any blood chemistry changes requiring more than 48 hours to resolve, resume at one dose level reduction				
		For any events of clinical TLS, resume at one dose level reduction following resolution				
Non-Hematologic Toxicit	ties					
Grade 3 or 4 non- hematologic toxicities	1 st occurrence	Interrupt venetoclax Once the toxicity has resolved to Grade 1 or baseline level, venetoclax therapy may be				

Event	Occurrence	Action				
		resumed at the same dose. No dose modification is required.				
	2 nd and subsequent occurrences	Interrupt venetoclax. Restart at one dose level reduction when resuming treatment with venetoclax after resolution. A larger dose reduction may occur the discretion of the investigator.				
Hematologic Toxicities						
Grade 3 or 4 neutropenia with infection or fever; or Grade 4 hematologic toxicities (except lymphopenia)	1 st occurrence	Interrupt venetoclax. To reduce the infection risks associated with neutropenia, granulocyte-colony stimulating factor (G-CSF) may be administered with venetoclax if clinically indicated. Once the toxicity has resolved to Grade 1 or baseline level, venetoclax therapy may be resumed at the same dose.				
	2 nd and subsequent occurrence	Interrupt venetoclax. Consider using G-CSF as clinically indicated. Restart at one dose level reduction when resuming treatment with venetoclax after resolution. Additional dose reductions may occu at the discretion of the physician. Re-escalation on the discretion of the treating physician				

Patients who require dose reductions to less than 100 mg for more than 4 weeks should stop treatment.

Management of Neutropenia

Nonclinical and clinical experience indicates that venetoclax may cause neutropenia. Subjects with a history of neutropenia or with significant bone marrow involvement may be at a particularly high risk.

Grade 3 or 4 neutropenia has been reported in patients treated with venetoclax. Complete blood counts should be monitored throughout the treatment period. Dose interruptions or dose reductions are recommended for patients with severe neutropenia. Supportive measures including antimicrobials for any signs of infection should be considered and prophylactic use of growth factors (e.g. G-CSF) is mandatory for patients with neutrophil counts below 1x10⁹/L.

Management of Hematologic Toxicities Other Than Neutropenia or Lymphopenia

Venetoclax treatment should be withheld for any Grade 4 hematologic toxicity. Once the toxicity has resolved to Grade 1 or baseline level (recovery), venetoclax may be re-started at the same dose administered prior to holding the drug. If the toxicity recurs, the dose reduction guidelines in

table I1 should be followed when resuming study treatment following resolution. Additional dose reductions may occur at the discretion of the physician.

Management of Non-Hematologic Toxicity

Venetoclax treatment should be withheld for any clinically relevant ≥ Grade 3 non-hematologic toxicity. Once the toxicity has resolved to Grade 1 or baseline level (recovery), venetoclax may be re-started at the same dose administered prior to holding the drug. If the toxicity recurs, the dose reduction guidelines in table I1 should be followed when resuming study treatment following resolution. Additional dose reductions may occur at the discretion of the physician.

3.11 CONCOMITANT THERAPY

3.11.1 Permitted Concomitant Therapy

Steroid treatment and moderate CYP3A inhibitors are permitted with the restrictions detailed below.

3.11.2 Prohibited or Restricted Concomitant Therapy

Patients who require the use of any of the prohibited therapies listed below will be discontinued from study treatment.

Use of the following therapies is prohibited during the study:

- Cytotoxic chemotherapy
- Radiotherapy
- Immunotherapy
- Any therapies intended for the treatment of leukemia whether FDA-approved or experimental (outside of this study)
- Anti-retroviral medications
- Warfarin and other vitamin K antagonists.

Please note: Patients being treated with Direct anti-coagulants (DOACs), acetylsalicylic acid and non-steroid anti-inflammatory drugs (NSAIDs) can be included but must be properly informed about the potential risk of bleeding under treatment with acalabrutinib.

Live-virus vaccines should not be given within 28 days prior to the initiation of study treatment, at any time during study treatment, or following study treatment until B-cell levels have returned to normal and any neutropenia have resolved.

Use of the following concomitant medications is prohibited:

- Steroid therapy for anti-neoplastic intent, with the exception of inhaled steroids for asthma, topical steroids, steroids up to 25 mg of prednisolone daily to control autoimmune phenomenon's, or replacement/stress corticosteroids.
- Strong CYP3A inhibitors (see appendix 3 for examples).

Concomitant medications that fall into the categories below could potentially lead to adverse reaction(s) and should be considered cautionary (except where noted). If a potential study patient is taking any of the medications in the categories described below, the investigator will assess and document the use of medications known or suspected to fall in the following medication categories:

- Moderate CYP3A inhibitors. Consider alternative agents with less CYP3A inhibition. If a moderate CYP3A inhibitor must be used, reduce the acalabrutinib dose to 100 mg once daily. At initiation and during the dose-titration phase, concomitant use of venetoclax with moderate CYP3A inhibitors should be avoided. Alternative treatments should be considered. If a moderate CYP3A inhibitor must be used, the initiation dose of venetoclax and the doses for the titration phase should be reduced by at least 50%. Patients should be monitored more closely for signs and symptoms of TLS. For patients who have completed the dose titration phase and are on a steady daily dose of venetoclax, the venetoclax dose should be reduced by 50% when used concomitantly with moderate CYP3A. Patients should be monitored more closely for signs of toxicities and the dose may need to be further adjusted. The venetoclax dose that was used prior to initiating the CYP3A inhibitor should be resumed 2 to 3 days after discontinuation of the inhibitor.
- Moderate and strong CYP3A inducers. Consider alternative treatments with less CYP3A induction.
- Weak CYP3A inhibitors and inducers
- P-gp substrates
- BCRP substrates
- OATP1B1/1B3 substrates
- P-gp inhibitors
- BCRP inhibitors
- OATP1B1/B3 inhibitors

A sample list of prohibited and cautionary medications that fall into these categories is provided in Appendix 3. It is not possible to provide a complete list of medications that fall into these categories, so if in question, please refer to the appropriate product label.

wanagement or	Potential Acalabrutinis	and venetociax interaction	ons with CTP3A inhibitors
	Ven	Acalabrutinib	
Inhibitors	Initiation and Ramp-Up Phase	Steady Daily Dose (After Ramp-Up Phase)	At any time
Strong CYP3A inhibitor	Prohibited		
Moderate CYP3A inhibitor		der alternative agent. If must stoclax dose by at least 50%	Avoid inhibitor use, consider alternative agent. If must be used, reduce acalabrutinib to 100 mg once daily

Management of Potential Acalabrutinib and Venetoclax Interactions with CYP3A Inhibitors

 In addition to these prohibited and cautionary medications, subjects should not consume grapefruit, grapefruit products, Seville oranges (including marmalade containing Seville oranges) or starfruits.

The concomitant use of strong inducers of CYP3A4 (see Appendix 3) should be avoided when possible. The concomitant use of strong inhibitors of CYP3A4 (see Appendix 3) is prohibited.

3.12 PRECAUTIONS

3.12.1 Dietary Restrictions

Acalabrutinib can be taken with or without food.

Patients should take venetoclax tablets orally once daily (in the morning). Each dose of venetoclax will be taken with approximately 240 mL of water during breakfast or first meal of the day. Patients should avoid consumption of foods or beverages containing grapefruit or Seville oranges or starfruit, as these contain certain ingredients that inhibit CYP3A activity.

3.12.2 Drug-Drug Interactions

At the systemic exposure levels expected in this study, acalabrutinib inhibition of CYP metabolism is not anticipated. However, acalabrutinib is metabolized by CYP3A. Concomitant administration with a strong CYP3A and P-glycoprotein (P-gp) inhibitor, itraconazole increased exposure by approximately 5-fold. Conversely, concomitant administration of with a strong CYP3A inducer, rifampin decreases acalabrutinib exposure and could reduce efficacy. Consequently, the concomitant use of strong inhibitors/inducers of CYP3A (see Appendix 3) should be avoided when possible.

Co-administration of 400 mg once daily ketoconazole, a strong CYP3A, P-gp and BCRP inhibitor, for 7 days in 11 previously treated patients with NHL increased venetoclax Cmax by 2.3-fold and AUC∞ by 6.4-fold. Co-administration of 50 mg once daily ritonavir, a strong CYP3A and P-gp

inhibitor, for 14 days in 6 healthy subjects increased venetoclax Cmax by 2.4-fold and AUC by 7.9-fold. Co-administration of venetoclax with other strong CYP3A4 inhibitors is predicted to increase venetoclax AUC by on average 5.8- to 7.8-fold.

Co-administration of a 600 mg single dose of rifampin, a P-gp inhibitor, in 11 healthy subjects increased venetoclax Cmax by 106% and AUC∞ by 78%. Concomitant use of venetoclax with P-gp and BCRP inhibitors at initiation and during the dose-titration phase should be avoided; if a P-gp and BCRP inhibitor must be used, patients should be monitored closely for signs of toxicities.

Co-administration of bile acid sequestrants with venetoclax is not recommended as this may reduce the absorption of venetoclax. If a bile acid sequestrant is to be co-administered with venetoclax, the SmPC for the bile acid sequestrant should be followed to reduce the risk for an interaction, and venetoclax should be administered at least 4-6 hours after the sequestrant.

If medically justified, subjects may be enrolled if such inhibitors or inducers can be discontinued or alternative drugs that do not affect these enzymes can be substituted within 7 days before first dose of study drug. If a subject requires a strong CYP3A4 while on study, the subject should be monitored closely for any potential toxicities.

The effect of agents that reduce gastric acidity (e.g., proton pump inhibitors or antacids) on acalabrutinib absorption was evaluated in a healthy volunteer study (ACE-HV-004). Results from this study indicate that subjects should avoid the use of calcium carbonate-containing drugs or supplements for a period of at least 2 hours before and at least 2 hours after taking acalabrutinib. Use of omeprazole, esomeprazole, lansoprazole or any other proton pump inhibitors while taking acalabrutinib is not recommended due to a potential decrease in study drug exposure. However, the decision to treat with proton-pump inhibitors during the study is at the investigator's discretion, with an understanding of the potential benefit to the subject's gastrointestinal condition and a potential risk of decreased exposure to acalabrutinib.

Although the effect of H2-receptor antagonists (such as famotidine or ranitidine) on acalabrutinib absorption has not been evaluated, if treatment with an H2-receptor antagonist is required, the H2-receptor antagonist should be taken approximately 2 hours after an acalabrutinib dose.

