Acalabrutinib is provided as hard gelatin capsules for oral administration approximately every 12 hours.

Venetoclax is provided as tablets for oral administration once daily

Concomitant Medications:

Prohibited Concomitant Therapy

[figure not shown]
Prohibited (strong CYP3A inhibitors and warfarin/vitamin K antagonists) and cautionary medications are defined as moderate CYP3A inhibitors, and moderate and strong CYP3A inducers.

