1.6.3 Warnings and Precautions

1.6.3.1 Tumor Lysis Syndrome (TLS)

Tumor lysis syndrome, including fatal events, has occurred in patients with previously treated CLL with high tumor burden when treated with venetoclax.

Venetoclax can cause rapid reduction in tumor, and thus poses a risk for TLS in the initial 5 weeks dose titration phase. Changes in electrolytes consistent with TLS that require prompt management can occur as early as 6 to 8 hours following the first dose of venetoclax and at each dose increase.

The risk of TLS is a continuum based on multiple factors, including comorbidities. Patients with high tumor burden (e.g., any lymph node with a diameter ≥5 cm or high ALC ≥25 x 109/l) are at greater risk of TLS when initiating venetoclax. Reduced renal function (CrCl <80 ml/min) further increases the risk. Patients should be assessed for risk and should receive appropriate prophylaxis for TLS, including hydration and anti hyperuricaemics. Blood chemistries should be monitored, and abnormalities managed promptly. Dosing should be interrupted if needed. More intensive measures (intravenous hydration, frequent monitoring, hospitalization) should be employed as overall risk increases. The instructions for "Prevention of tumor lysis syndrome" should be followed.

Concomitant use of this medicinal product with strong or moderate CYP3A inhibitors increases venetoclax exposure and may increase the risk for TLS at initiation and during the dose-titration phase. Also inhibitors of P-gp or BCRP may increase venetoclax exposure. In the initial Phase 1 dose-finding studies, which had a shorter (2 to 3 week) titration phase and higher starting dose, the incidence of TLS was 13% (10/77; 5 laboratory TLS; 5 clinical TLS), including 2 fatal events and 3 events of acute renal failure, 1 requiring dialysis.

The risk of TLS was reduced after revision of the dosing regimen and modification to prophylaxis and monitoring measures. In venetoclax clinical studies, patients with any measurable lymph node \geq 10 cm or those with both an ALC \geq 25 x 10 9 /l and any measurable lymph node \geq 5 cm were hospitalized to enable more intensive hydration and monitoring for the first day of dosing at 20 mg and 50 mg during the titration phase.

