3.6.2 Exclusion Criteria

Subjects will be ineligible for this study if they meet any of the following criteria:

- 1. Prior CLL treatment (including monoclonal antibodies, chemotherapy, small molecules, including CD20 antibodies, BTK inhibitors and bcl-2 inhibitors for any indication)
- 2. Transformation of CLL (Richter's transformation)

- 3. Previous autoimmune disease as AIHA (autoimmune hemolytic anemia) or ITP (idiopathic thrombocytopenic purpura) treated with immune suppression or uncontrolled AIHA or ITP
- 4. History of progressive multifocal leukoencephalopathy
- 5. HIV infection (a negative test required)
- 6. Known active infection
- Malignancies other than CLL requiring systemic therapies (except anti-hormonal therapies) or considered to impact survival
- 8. Requirement of therapy with strong CYP3A4 and CYP3A5 inhibitors/inducers or anticoagulant therapy with vitamin K antagonists
- 9. History of bleeding disorders or current platelet inhibitors or anticoagulant therapy
- 10. History of clinically significant cardiovascular disease such as arrhythmias, congestive heart failure, or myocardial infarction within 6 months of screening, or any Class 3 or 4 cardiac disease as defined by the New York Heart Association Functional Classification, or corrected QT interval (QTc) > 480 msec at screening.
- 11. History of stroke or intracranial hemorrhage within 6 months prior to registration.
- 12. Use of investigational agents which might interfere with the study drug within 28 days prior to registration.
- 13. Vaccination with live vaccines within 28 days prior to registration.
- 14. Major surgery less than 30 days before start of treatment. Note: If a subject had major surgery, they must have recovered adequately from any toxicity and/or complications from the intervention before the first dose of study drug.
- 15. Known hypersensitivity to any active substance or to any of the excipients of one of the drugs used in the trial.
- 16. Pregnant women and nursing mothers (a negative pregnancy test is required for all women of childbearing potential within 7 days before start of treatment; further pregnancy testing will be performed regularly).

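### Section 3.12.2 only discourages strong CYP3A inhibitors, although the synopsis, section 3.11.2 and Appendix 3 prohibit them

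*Protocol*

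**What the plan says.** **Section 3.12.2 (Drug-Drug Interactions).** After describing the effect of itraconazole and rifampin on acalabrutinib, it concludes that "the concomitant use of strong inhibitors/inducers of CYP3A (see Appendix 3) should be avoided when possible". After the venetoclax interaction data it allows enrolment if such inhibitors or inducers can be stopped or replaced within 7 days before the first dose. It then adds: "If a subject requires a strong CYP3A4 while on study, the subject should be monitored closely for any potential toxicities". The word inhibitor or inducer is missing from that sentence.

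**Everywhere else that sets a rule for use on treatment.** The synopsis, under concomitant medications, has "Prohibited (strong CYP3A inhibitors and warfarin/vitamin K antagonists) and cautionary medications are defined as moderate CYP3A inhibitors". Section 3.11.2 puts strong CYP3A inhibitors on its list of prohibited concomitant medications, repeats the prohibition in its interaction table, and closes with one sentence telling sites to avoid strong inducers if they can and another prohibiting strong inhibitors. Appendix 3 repeats the prohibition in its opening sentence and column heading, and labels the CYP3A inhibitor column as applying to both study drugs.

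**Consequence of need.** Section 3.11.2 opens with: "Patients who require the use of any of the prohibited therapies listed below will be discontinued from study treatment". At entry, exclusion criterion 8 already removes patients with "Requirement of therapy with strong CYP3A4 and CYP3A5 inhibitors/inducers or anticoagulant therapy with vitamin K antagonists".

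**The concern.** A site consulting the section titled for drug interactions finds a rule that leaves room for a strong CYP3A inhibitor when there is no alternative. A site consulting 3.11.2 or Appendix 3 finds a ban. The two instructions cannot both be followed.

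The situation is foreseeable. Patients are selected in part for infection risk, and section 1.6.3.2 and the neutropenia guidance in 3.10.2 ask sites to consider antimicrobials for signs of infection. Appendix 3 lists clarithromycin, itraconazole, posaconazole and voriconazole among the strong inhibitors. Exclusion 8 screens for need at entry; a need that arises later falls to the sections that disagree.

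Patient safety is at stake. Section 1.6.3.1 says that use with "strong or moderate CYP3A inhibitors increases venetoclax exposure and may increase the risk for TLS at initiation and during the dose-titration phase". These patients do not meet IWCLL treatment criteria and would otherwise be observed, so there is little room for avoidable toxicity.

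**Working it through.** The check is a comparison of wording; the plan states no figure to reproduce.

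**1. Is the difference one of substance?** A drug to be avoided if possible may be given when avoidance is not possible. A prohibited drug may not. The closing lines of 3.11.2 show that the protocol itself uses the two terms for different classes: the softer one for strong inducers, the ban for strong inhibitors. Section 3.12.2 joins the classes with a slash and applies the inducer rule to both. For inducers it agrees with 3.11.2; for inhibitors it does not.

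**2. Does the first paragraph escape because it argues from acalabrutinib?** No. Both drugs are given together from cycle 1 day 1, and the prohibition in 3.11.2 and Appendix 3 covers both.

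**3. What does the monitoring sentence mean?** The sentence before it speaks of inhibitors or inducers, and toxicity is the hazard of an inhibitor, so inhibitors are the likelier reading. On that reading, the instructions compare as follows:

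| Class needed on treatment | Acalabrutinib | Venetoclax | Source |
|---|---|---|---|
| Moderate inhibitor | 100 mg once daily | at least 50% lower in titration, 50% lower at steady dose | 3.11.2 |
| Strong inhibitor | prohibited | prohibited | 3.11.2, Appendix 3 |
| Strong inhibitor, if that is the missing noun | monitor | monitor | 3.12.2 |

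The stronger class would then get the weaker precaution.

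**4. How large is the hazard if one is given?** All figures are as printed in 3.12.2:
- Prediction for venetoclax: "Co-administration of venetoclax with other strong CYP3A4 inhibitors is predicted to increase venetoclax AUC by on average 5.8- to 7.8-fold".
- Ketoconazole, 7 days, 11 patients: venetoclax AUC 6.4-fold, Cmax 2.3-fold.
- Ritonavir: "for 14 days in 6 healthy subjects increased venetoclax Cmax by 2.4-fold and AUC by 7.9-fold".
- Itraconazole: acalabrutinib exposure about 5-fold.

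**5. How wide is the window?** Treatment lasts 3 cycles × 28 days = 84 days. Venetoclax ramp-up covers 5 dose levels × 7 days = 35 of those days, the period for which section 1.6.3.1 names the tumor lysis risk. The planned treatment arm has 25 patients. The protocol gives no rate at which they would need a strong inhibitor, so no expected number of exposed patients can be calculated.

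**The case against.** The best defence is that the protocol already directs readers to the right rule. Sections 1.3.3 and 1.5.3, both about interaction potential, refer to the Concomitant Therapy section, which contains the ban. The disputed sentence itself points to Appendix 3, where the strong inhibitors appear under a heading marked as prohibited. A site would have to overlook that heading, 3.11.2 and the synopsis to go wrong. This stands as a reason to think an error less likely. It does not settle which text governs: no order of precedence is stated, and section 3.7.3 sends sites to 3.12.2 as working guidance for gastric-pH agents, so 3.12.2 is not mere background.

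Four stronger readings are tempting and should not be adopted:
- **A reader might infer that 3.12.2 plainly permits co-administration under monitoring.** The monitoring sentence lacks its noun and refers to being on study. Under section 3.13, patients who stop treatment remain in follow-up, so the sentence could describe monitoring after the drugs are stopped. The firm contradiction rests on the first-paragraph sentence alone.
- **A reader might infer that 3.11.2 mandates discontinuation beyond doubt.** Its discontinuation sentence speaks of prohibited therapies listed below and is followed by two lists, one of therapies and one of concomitant medications. Strong inhibitors are in the second. The natural reading covers both lists, but a narrow reading is possible. The prohibition conflicts with 3.12.2 either way.
- **A reader might infer that the inducer rule is also wrong.** The avoid-if-possible rule for strong inducers matches 3.11.2.
- **A reader might infer an effect on the primary comparison.** Nothing in the protocol supports one, and the exposure multiples describe the hazard of co-administration, not the chance that this wording leads to it.

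**Conclusion.** The point holds in limited form. Section 3.12.2 states a weaker rule for strong CYP3A inhibitors than the synopsis, section 3.11.2 and Appendix 3, and the two cannot be reconciled. Its monitoring sentence is defective and, if it concerns inhibitors, asks for less than 3.11.2 requires for moderate ones.

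The hazard of co-administration is large by the protocol's own data, while the opportunity for it is narrow: a need first arising on treatment, at a site that relies on 3.12.2 despite the cross-references. How often that would happen is unknown. The conclusion assumes that the ban, which is repeated consistently, is the intended rule. It is a consistency error with a patient-safety consequence and should be corrected; the design and analysis are untouched.

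**What to change.** Change section 3.12.2 only.

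1. Replace the concluding sentence of the first paragraph with: *Consequently, strong CYP3A inhibitors are prohibited during study treatment (section 3.11.2, Appendix 3); strong CYP3A inducers are to be avoided where possible.*
2. Keep the 7-day substitution rule and replace the monitoring sentence with: *If a strong CYP3A inhibitor becomes necessary during study treatment, it must not be given together with acalabrutinib or venetoclax; study treatment is discontinued per section 3.11.2 and follow-up continues per section 3.13.*
3. Do not transfer the toxicity-monitoring instruction to inducers. By sections 1.6.3.3 and 3.12.2 they lower exposure, so the concern is loss of efficacy. Say so, and refer to the advice in 3.11.2 to consider alternatives with less induction.

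If the sponsor would rather allow a temporary hold for a short anti-infective course, that is a clinical choice, but it must be written into both 3.11.2 and 3.12.2.

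The cost is two reworded sentences and a short addition on inducers, plus a matching edit in 3.11.2 if a hold is chosen. No new data, visits or patients are needed.
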